STATISTICAL ANALYSIS	23
Modified Intent-to-Treat Population.....	23
Safety Population	23
PRIMARY ENDPOINT	23
SECONDARY ENDPOINTS.....	24
EXPLORATORY ENDPOINTS	24
SAFETY ENDPOINTS	24
COLLECTION AND DERIVATION OF ENDPOINTS.....	24
Primary Efficacy Variable	24
Secondary Efficacy Variables.....	25
APPENDIX I	26
APPENDIX II.....	27

**A MULTICENTER, RANDOMIZED, DOUBLE-BLIND, PLACEBO-CONTROLLED
STUDY EVALUATING THE EFFICACY AND SAFETY OF MLD10 IN THE
PREVENTION OF MIGRAINE HEADACHE IN ADULTS**

INDICATION

For the prophylaxis of migraine headaches in adults

STUDY PURPOSE

- To evaluate the daily use of MLD10 and placebo for the treatment of migraine, as measured by the change from baseline in the number of migraine headache days of subjects treated for 3 months.
- To compare daily use of MLD10 and placebo as measured by:
 - change in the quantitative and qualitative aspects of migraine headaches from baseline, during treatment, and at the conclusion of a 3-month treatment period.
 - safety and tolerability measures in migraine headache subjects through the monitoring of adverse events (AEs) and clinical chemistry values.

SUMMARY OF STUDY DESIGN

This is a double-blind, placebo-controlled, randomized, multi-center study. Subjects agreeing to participate in the study and meet the entry criteria assessed at the screening visit, will begin a 28 day baseline period to confirm their diagnosis, as well as establish baseline migraine characteristics. During this baseline period, subjects will continue treating their migraines as usual, simply recording the information in a daily headache diary. Subjects who, after completing the baseline, continue to meet entrance criteria will be eligible to enter into the treatment phase and be randomized according to the Clinvest generated randomization schedule. Approximately 142 subjects (71 subjects per arm) will be randomized and enter the treatment phase receiving MLD10 or placebo in a 1:1 design at a maximum of 8 US sites. Diary assessments will collect study medication adherence, pain severity, headache symptoms, acute medication usage, and unusual symptoms. Serum samples will be collected and analyzed for ionized Mg, electrolytes, and creatinine.

The study consists of 5 visits:

Baseline Period:	Visit 1 (Screening/Baseline Period)
Treatment Period:	Visit 2 (Randomization/Treatment Period Month 1)
	Visit 3 (Treatment Period Month 2)
	Visit 4 (Treatment Period Month 3)
	Visit 5 (Final Visit)

POPULATION SAMPLE

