11. has significant risk of suicide, defined as a "yes" answer to any of the following questions on the Columbia-Suicide Severity Rating Scale (C-SSRS), either at the screening visit (when assessing the prior 12 months) or at visit 2 (when assessing time since the screening visit):
 - a. Questions 4 or 5 on the suicidal ideation section
 - b. Any question on any item in the suicidal behavior section
12. any psychiatric disorder with psychotic features, and/or any other psychiatric disorder not stable or well controlled, that would interfere in their ability to complete study activities.
13. hypersensitivity, intolerance, or contraindication to the use of magnesium L-lactate dehydrate or any of its components.
14. received any investigational agents within 30 days prior to Visit 1.
15. plans to participate in another clinical study at any time during this study.

STUDY DESIGN

This is a multi-center, double-blind, randomized, placebo-controlled, parallel study of MLD10 for the prevention of migraine headache. The study population will consist of approximately 142 male and female subjects between 18 and 65 years of age with frequent episodic migraine as defined by ICHD-3 beta criteria. Two MLD10 (243 mg of elemental magnesium) or placebo caplets will be taken twice daily for a total daily dose of 486 mg.

INFORMED CONSENT

The investigator must obtain documented consent from each potential subject, or legally authorized representative, prior to any study related procedures being performed. Consent must

be documented by the subject's dated signature on an Informed Consent Form (ICF) along with the dated signature of the persons conducting the consenting process. A copy of the signed and dated consent form should be given to the subject before participating in the study.

If the subject is illiterate, an impartial witness should be present during the entire informed consent reading and discussion. Afterward, the subject should sign and date the informed consent, if capable. The impartial witness should also sign and date the informed consent along with the person conducting the consent process.

VISIT 1 - SCREENING

The following will be completed at Visit 1:

1. Obtain written Informed Consent. The informed consent will be obtained in accordance with Good Clinical Practices (GCP) and all applicable regulatory requirements from each subject prior to participation in the study.

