2. Verify Inclusion/Exclusion Criteria. Subjects will meet all the inclusion and none of the exclusion criteria.
3. Obtain demographics (race, ethnicity, sex, date of birth)
4. Obtain medical, medication, and headache history. Data collected will include medical history and diagnoses, age at onset of migraine and other pertinent migraine/headache history, history of acute and prophylactic headache medications within the past 30 days, and history of other recent/concomitant medications.
5. Obtain date of last menstrual cycle and perform urine pregnancy test, if appropriate. Results of the pregnancy test must be negative to continue in study.
6. Perform physical and neurological examinations.
7. Measure vital signs (height, weight, resting heart rate, and blood pressure).
8. Review Baseline Headache Diary. Subjects will be instructed to complete a daily online headache diary. Assessments to be captured are start/stop time, severity, associated symptoms, use of rescue medications, and unusual symptoms.
9. Administer Columbia-Suicide Severity Rating Scale (C-SSRS).
10. Schedule Visit 2.

VISIT 2 - RANDOMIZATION

1. Verify Inclusion/Exclusion Criteria. Subjects must continue to meet all inclusion (including ≥ 3 days of migraine during baseline) and none of the exclusion criteria.
2. Perform urine pregnancy test, if appropriate. Results of the pregnancy test must be negative to continue in study.
3. Measure vital signs (weight, resting heart rate, and blood pressure).
4. Record any changes to concomitant medications.
5. Record any Serious Adverse Events (SAE) since signing the Informed Consent.
6. Review Baseline Headache Diary for completeness and continuing eligibility.
7. Randomize subject
8. Review Month 1 Headache Diary instructions (same instructions as those discussed for Baseline Headache Diary).
9. Dispense Month 1 study medication. Subjects will be instructed how to take study medication, prohibited medications, dosage limitations of study medication, and storage requirements. Subjects will be instructed to return all used/partially

used/unused study medication at next office visit and medications reconciliation will be performed to ensure a compliance of at least 80%. Subjects not complying at an 80% level will be withdrawn, unless otherwise approved by the Sponsor and/or Clinvest. (Estimated to be < 10%)

10. Administer C-SSRS.
11. Administer MIDAS.
12. Collect serum samples for electrolytes, creatinine, and ionized Mg.
13. Schedule Visit 3.

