Table 1. Study Procedures

	Screening	Randomization	Treatment		
	Visit 1 Day 0	Visit 2 Day 29 (+/- 3)	Visit 3 Day 58 (+/- 3)	Visit 4 Day 87 (+/- 3)	Visit 5 Day 116 (+/- 3)
Informed Consent	X				
Physical/Neurological Exam	X				X
Vital Signs	X	X	X	X	X
Verify Inclusion/Exclusion	X	X			
Subject Randomization		X			
Medical History	X				
Migraine History	X				
Medication History	X				
Update Medications		X	X	X	X
Urine Pregnancy Test	X	X	X	X	X
SGIC					X
PGIC					X
Dispense Study Medication		X	X	X	
Drug Accountability			X	X	X
Headache Diary	X	X	X	X	
Review Diary		X	X	X	X
Collect Adverse Events		X	X	X	X
Administer C-SSRS	X	X	X	X	X
Administer MIDAS		X			X
Serum Electrolytes & Creatinine		X	X	X	X
Serum Ionized Mg		X	X	X	X

STUDY MEDICATION RANDOMIZATION

Eligible subjects will be randomized 1:1 to receive magnesium L-lactate dehydrate (243 mg of elemental mg⁺⁺ BID for a total of 486mg daily) or placebo at Visit 2. If at any time during the

study the subject withdrawals from the study, they will be instructed to return all used packaging and unused medication.

Group A

Subjects randomized to MLD10 (Group A) will be dispensed a 28 day supply of magnesium L-lactate dehydrate 10 mEq (121.5 mg of elemental mg⁺⁺ caplets) for daily treatment. A total of 120 caplets will be given each time at Visit 2, 3, and 4. Additional overage will be given to account for the 3 day window. Subjects will be instructed to take two caplets of study medication BID at about the same time each day (i.e. 8AM & 8PM for a total of 486mg's of elemental mg⁺⁺ per day). Subjects will be instructed regarding storage requirements and will be asked to return all used/partially used/unused medication containers at the next office visit.

Group B

Subjects randomized to placebo (Group B) will be dispensed a 28 day supply of matching placebo for daily treatment. A total of 120 caplets will be given each time at Visit 2, 3, and 4. Additional overage will be given to account for the 3 day window. Subjects will be instructed to take two caplets of study medication BID at about the same time each day (i.e. 8AM & 8PM). Subjects will be instructed regarding storage requirements and will be asked to return all used/partially used/unused medication containers at the next office visit.

RESCUE MEDICATION

Subjects will be instructed they may take their investigator approved rescue medications for headaches, if needed. Rescue medication usage and dosage will be recorded on the headache diary.

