The C-SSRS will be conducted at the screening visit and each subsequent office visit. The C-SSRS is a semi-structured interview designed to assess the severity and intensity of suicidal ideation, suicidal behavior, and non-suicidal self-injurious behavior over a specified time period (e.g., prior year, since last visit). The measurement of suicidal ideation is based on 5 “yes” or “no” questions (plus a description if answered “yes”) arranged in order of increasing severity. If the patient answers “yes” to either question 1 or 2, the intensity of ideation will then be assessed in 5 additional questions relating to the frequency, duration,

controllability, deterrents, and reasons for the most severe ideation. Suicidal behavior is then assessed by asking further questions to categorize the behaviors into actual, aborted, and interrupted attempts; preparatory behavior; and non-suicidal self-injurious behavior. The interview is used in full only if the initial questions are positive; this assessment is completed at all scheduled clinic visits at which other clinical assessments are to be carried out.

If any item(s) on the C-SSRS are answered with “yes”, a clinician investigator must review patient’s responses in order to:

- a) at screening and baseline determine patient’s study eligibility and potential need for referral to a mental health professional AND
- b) during the study evaluate patient’s need for appropriate medical management such as referral to a mental health professional.

A significant risk of suicide is defined as a “yes” in answer to:

- a) questions 4 or 5 on the suicidal ideation section; OR
- b) any questions on any item in the suicidal behavior section.

This must be reported as a serious adverse event and followed up accordingly. Additionally, if a patient responds “yes” to any of the suicidal ideation questions 1 to 3, a clinician investigator should apply clinical judgment to determine the need for reporting as an adverse event or serious adverse event and the need for any referral.

SUMMARY OF METHODS OF DATA COLLECTION

Data required for the evaluation of the primary and some secondary measures will be recorded by subjects using a daily e-diary. The following data will be collected daily with the e-diary (subject instructions and training for completion of the e-diary will be provided):

- Estimated total duration of headache that day (if no headache, subject will report 0 hours)

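### Minor: at Visit 2 the C-SSRS decides eligibility, but the procedure list places it after randomization and dispensing

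*Protocol*

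**What the plan says.** Exclusion criterion 11 defines significant suicide risk as a positive answer to ideation question 4 or 5, or to any item on suicidal behavior. It applies the criterion at two time points: "either at the screening visit (when assessing the prior 12 months) or at visit 2 (when assessing time since the screening visit". The C-SSRS section under Safety Measures agrees: a clinician investigator must review any positive answer, and at screening and baseline the purpose of that review is to settle eligibility.

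The section Visit 2 - Randomization gives a numbered list of 13 items. Verification of the entry criteria is item 1, "Randomize subject" is item 7, dispensing of the Month 1 supply is item 9, and "Administer C-SSRS" is item 10.

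Two other sections restrict who may be randomized. The Summary of Study Design says that subjects who "continue to meet entrance criteria will be eligible to enter into the treatment phase and be randomized". Study Medication Randomization says "Eligible subjects will be randomized 1:1 to receive magnesium L-lactate dehydrate". On supply, the same section says for each group "A total of 120 caplets will be given each time at Visit 2, 3, and 4".

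**The concern.** A test that decides entry has to be done and read before allocation. Because the Visit 2 interview covers the time since screening, its result cannot be known from Visit 1. If a site uses the list as a checklist, a subject can be allocated and supplied before the question that would exclude them is asked. The site would then have a randomized subject who should not have entered, and would have to recover study medication from a person just identified as being at significant risk of suicide. What is at stake is clean conduct of a safety exclusion, not the estimate of treatment effect.

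**Working it through.** The Protocol states no figure to reproduce. The check sets its sections side by side.

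**1. Does the Visit 2 C-SSRS decide eligibility?** Yes. Exclusion criterion 11 names Visit 2, and the C-SSRS section assigns the review at baseline to eligibility.

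**2. Where does it stand in the Visit 2 list?**

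| Item | Procedure | Bears on eligibility at this visit? |
|---|---|---|
| 1 | Verify entry criteria | Yes, overall check |
| 2 | Pregnancy test | Yes, must be negative |
| 6 | Baseline diary review | Yes, completeness and eligibility |
| 7 | Randomization | Allocation |
| 9 | Dispensing | Supply |
| 10 | C-SSRS | Yes, exclusion criterion 11 |

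The C-SSRS stands 10 - 7 = 3 places after randomization and 10 - 9 = 1 place after dispensing. Of the separate assessments in the table that bear on eligibility, it is the only one listed after allocation. Unlike the pregnancy test, its entry carries no statement that the result governs continuation.

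**3. Does anything else fix the order?** No. Table 1 marks the C-SSRS at Visit 2 but gives no order within the visit, and no section says that it must precede randomization.

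**4. Does the same placement matter at the other visits?** No. At Visit 1, "Administer Columbia-Suicide Severity Rating Scale (C-SSRS") is item 9, and only the scheduling of Visit 2 follows it. At Visits 3 to 5 it is again item 10, but there it monitors safety and does not decide entry. Only at Visit 2 do allocation and supply come before a result that should govern them.

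**5. What has been handed over by item 10?** 120 caplets. At 2 caplets twice daily, or 4 per day, that is 120 / 4 = 30 days. The Protocol calls this a 28-day supply (28 x 4 = 112 caplets) and mentions additional overage for the visit window.

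**The case against.** The strongest reply is that the governing rule is stated correctly. Item 1 at Visit 2 requires that no exclusion criterion is met, and criterion 11 is one of them, so item 1 cannot properly be completed without the C-SSRS result. Two further sections confine randomization to eligible subjects. Nor does the list behave as a strict sequence: verification precedes its own inputs at Visits 1 and 2, and drug accountability follows dispensing at Visits 3 and 4. At Visit 2, MIDAS and the serum samples also follow dispensing, although they supply pre-treatment values.

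Much of this stands. A reader might infer that the Protocol tells sites to randomize subjects before their eligibility is known. The documents do not support that: the list is not declared chronological, and no sentence permits randomization of an ineligible subject. What remains is that the list puts the pregnancy test and diary review before allocation and the C-SSRS after it. MIDAS and the serum samples are not a true parallel, because neither is named in the entry criteria.

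The harm is also bounded. It needs a site that follows the list literally and a new excluding answer since screening. The Protocol does not say that the first dose is taken in clinic. A subject found at item 10 and never dosed would fall outside both the mITT and safety populations, since each requires at least one dose.

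A reader might also infer from "The interview is used in full only if the initial questions are positive" that sites may skip the behavior items when ideation is denied, which would disable part of criterion 11. The Protocol does not identify the initial questions, so that reading is possible. However, the only express condition, a positive answer to question 1 or 2, is attached to the intensity questions. The next sentence says without a condition of its own that behavior is then assessed, and the skip reading would defeat the criterion that rests on those items. This is at most a wording clarification.

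**Conclusion.** The point holds as a minor one, a free improvement. The Visit 2 list sits badly with exclusion criterion 11, because an assessment that decides entry is listed after allocation and supply. Its size is one misplaced list item. The consequence, for any subject affected, is one allocation used and one supply of 120 caplets to recover.

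This rests on two assumptions: that baseline in the C-SSRS section means Visit 2, as criterion 11 indicates, and that some sites would use the numbered list as a working checklist. The Protocol gives no rate of excluding answers between screening and Visit 2, and none is assumed here. No effect on the analysis, power or alpha is claimed.

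**What to change.** In Visit 2 - Randomization, move the C-SSRS, together with the clinician investigator's review of any positive answer, ahead of randomization. Placed directly after the diary review, it becomes item 7; randomization becomes item 8, the diary instructions item 9 and dispensing item 10. Items 11 to 13 are unchanged. A short clause that the subject may be randomized only if criterion 11 is not met would match the wording already used for the pregnancy test.

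The cost is one list item moved. The instrument, visits, staff and number of assessments stay the same.

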To compare the change from baseline of subjects treating with MLD10 versus placebo on the following parameters during a 3 month treatment period.

- migraine with aura days
- serum ionized magnesium

SAFETY OBJECTIVES

Safety assessments will include monitoring the parameters during the length of the study.

- adverse events
- physical examination
- urine pregnancy tests for all females of childbearing potential

- vital signs including blood pressure, pulse rate, and weight
- Columbia-Suicide Severity Rating Scale (C-SSRS)
- concomitant medications
- clinical chemistry measurements

SUBJECT SELECTION

Approximately 142 subjects will be randomized from the clinic and general population with a history of mild to severe migraine, with or without aura, that meets the International Classification of Headache Disorders (ICHD-3 beta) definition for episodic migraine with a frequency of 3-14 days of migraine (or headache treated with migraine specific medication) per month. Subjects will have a stable history of headaches meeting the above parameters for at least 3 months prior to enrollment. Subjects on migraine preventative medications will be required to be on a stable regimen for 30 days prior to and throughout the study period.

POWER ANALYSIS

A power analysis, using GPower Version 3.1.7, indicated a total sample size of 128 subjects would be needed to detect medium effects ($d = .25$) with 80% power using an analysis of covariance (ANCOVA) test to include fixed effects, main effects, and interactions with alpha being .05. Given an estimated 10% early termination rate, a total estimated sample size of 142 subjects is needed.

INCLUSION CRITERIA

Subjects must meet the following inclusion criteria:

1. male or female, in otherwise good health, 18 to 65 years of age.
2. history of frequent episodic migraine (3-14 migraine days per month) (with or without aura) according to the ICHD-3 beta for at least 3 months.
3. onset of migraine before age 50.
4. stable history of migraine at least 3 months prior to screening.
5. not currently taking a migraine preventive or has been taking preventive for at least 30 days prior to screening and agrees to not start, stop, or change medication and/or dosage during the study period.
6. if female of childbearing potential, has a negative urine pregnancy test at Visits 1-5 and uses, or agrees to use, for the duration of the study, a medically acceptable form of contraception as listed:

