VISIT 3 - END OF TREATMENT PERIOD MONTH 1

1. Record any changes to concomitant medications.
2. Record any Non-Serious Adverse Events (NSAE) and/or SAEs.
3. Perform urine pregnancy test, if appropriate. Results of the pregnancy test must be negative to continue in study.
4. Measure vital signs (weight, resting heart rate, and blood pressure).
5. Review Month 1 Headache Diary for completeness.
6. Review instructions for Month 2 Headache Diary (same instructions as those discussed for Month 1 Headache Diary).
7. Collect Month 1 unused study medication and used packaging. Confirm 85% compliance of medication usage per study protocol.
8. Dispense Month 2 study medication and review the dosage limitations of study medication, storage requirements, and to return all used/partially used/unused study medication at next office visit.
9. Perform drug accountability.
10. Administer C-SSRS.
11. Collect serum samples for electrolytes, creatinine, and ionized Mg.
12. Schedule Visit 4.

VISIT 4 - END OF TREATMENT PERIOD MONTH 2

1. Record any changes to concomitant medications.
2. Record any NSAEs/SAEs.
3. Perform urine pregnancy test, if appropriate. Results of the pregnancy test must be negative to continue in study.
4. Measure vital signs (weight, resting heart rate, and blood pressure).
5. Review Month 2 Headache Diary for completeness.
6. Review instructions for Month 3 Headache Diary (same instructions as those discussed for Month 2 Headache Diary).
7. Collect Month 2 unused study medication and used packaging. Confirm 85% compliance for medication usage per study protocol.
8. Dispense Month 3 study medication and review the dosage limitations of study medication, storage requirements, and to return all used/partially used/unused study medication at next office visit.
9. Perform drug accountability.
10. Administer C-SSRS.
11. Collect serum samples for electrolytes, creatinine, and ionized Mg.
12. Schedule Visit 5.

VISIT 5 - END OF TREATMENT PERIOD MONTH 3

1. Record any changes to concomitant medications.
2. Record any NSAEs/SAEs.
3. Perform urine pregnancy test, if appropriate.
4. Measure vital signs (weight, resting heart rate, and blood pressure)
5. Perform physical/neurological examinations.
6. Collect Month 4 unused study medication and used packaging.
7. Perform drug accountability.
8. Administer SGIC & complete PGIC.
9. Administer MIDAS.
10. Administer C-SSRS.
11. Collect serum samples for electrolytes, creatinine, and ionized Mg.
12. Exit subject.

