At randomization (Visit 2), neither the subject nor the investigator will be aware to which treatment group the subject has been assigned. If needed, for safety and proper treatment of the subject, the investigator can unblind the subject's treatment assignment to determine which treatment has been assigned and institute appropriate follow-up care. When possible, Clinvest should be notified prior to unblinding study medication.

Individual unblinding envelopes are shipped with study medication. Each study medication kit has a corresponding unblinding envelope. Unblinding will include matching the kit and unblinding envelope with the subject drug number.

To unblind a subject without breaking the blind for remaining subjects' treatment the following instructions described below will be followed:

- Obtain the security envelope containing the unblinding envelopes.
- Remove the unblinding envelope with the study drug number corresponding with the study medication kit dispensed to the subject.
- Break the seal of the unblinding envelope and remove the subjects' treatment label.
- Return the subjects' treatment label to the unblinding envelope.
- Return the unblinding envelope to the security envelope.
- Document on the unblinding form located in the eAdmin Binder.
- Email copy of unblinding form to [contact] within 24 hours of unblinding.
- Complete and email or fax the Sterling IRB, unanticipated problem report form, to Sterling IRB within 10 business days of unblinding.

DISCONTINUATION/WITHDRAWAL FROM STUDY

All subjects who withdraw from the study, for any reason, must return all study medication and supplies to the investigator or his/her delegate at the first available opportunity.

Subjects may withdraw at any time or be dropped from the study at the discretion of the investigator or Clinvest if he/she violates the study plan or for administrative and/or safety reasons. When a subject discontinues/withdraws prior to study completion, all applicable activities scheduled for the final study visit should be performed at the time of discontinuation, as well as the completion of the early termination form and unscheduled visit form (if appropriate). Any adverse experiences which are present at the time of discontinuation/withdrawal should be followed in accordance with the safety requirements outlined in the adverse event reporting section of this protocol.

REPORTING PREGNANCY

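### Subjects withdrawn for low medication compliance stop the e-diary, so their month-3 primary value is replaced by baseline although it could have been observed; the compliance trigger is also stated inconsistently

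*Protocol*

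**What the plan says.** All references are to the Protocol.

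- **Compliance rule.** Visit 2, item 9, where Month 1 medication is dispensed, says: "Subjects not complying at an 80% level will be withdrawn, unless otherwise approved by the Sponsor and/or Clinvest". It gives the expected share as "Estimated to be < 10" per cent. No criterion for the approval is given.
- **Later checks.** Visit 3, item 7 reads "Collect Month 1 unused study medication and used packaging. Confirm 85% compliance of medication usage per study protocol", and Visit 4, item 7 reads "Collect Month 2 unused study medication and used packaging. Confirm 85% compliance for medication usage per study protocol". Neither states what follows from a failed check. Visit 5 has drug accountability but no threshold. Its collection item, "Collect Month 4 unused study medication and used packaging", carries the wrong month label.
- **Plan violators.** Under Discontinuation/Withdrawal from Study, a subject may "be dropped from the study at the discretion of the investigator or Clinvest if he/she violates the study plan".
- **After withdrawal.** The same section brings the final-visit activities forward to the time of discontinuation. No section continues the e-diary.
- **Primary time point and missing values.** Primary Efficacy Variable fixes treatment month 3, the last 28 days. The imputation paragraph (under Safety Population) carries the baseline value forward for anyone who discontinues and classes that subject as a non-responder. The mITT population needs one dose and one post-treatment measurement.
- **Sample size.** Power Analysis: "Given an estimated 10% early termination rate, a total estimated sample size of 142 subjects is needed".

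**The concern.** Adherence is observed after randomisation. A subject may take fewer caplets because of side effects or because the headaches have not improved, and either reason may be more common in one arm. The rule makes that behaviour a reason to leave the study, not just something to record. Leaving the study ends the e-diary, although the diary is completed online at home and does not depend on taking study medication.

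A month-3 outcome that could have been observed is therefore replaced by an assumed change of zero. If both arms lose the same share, the treatment difference is diluted. If the shares differ, the difference shifts in a direction that cannot be known in advance. A statistical analysis plan can choose another imputation, but it cannot recover diary days that the Protocol stops collecting.

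Two further features make the rule hard to apply evenly. The threshold is 80% in one place and 85% in two others. Non-compliance in months 1 or 2 can also lead to a baseline value, whereas non-compliance in month 3 leaves the observed value in place.

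**Working it through.** **1. The plan's own figures.** The stated 128 reproduces for a two-group ANCOVA with one covariate, Cohen's f = 0.25 and two-sided alpha 0.05 (power 0.801). For two equal groups this is a difference of 0.50 SD. (The Protocol labels the 0.25 as d, which is a separate matter.) Allowing for 10% loss, 128 / 0.90 = 142.2, which matches the stated 142.

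**2. How many subjects.** The ceiling of the Protocol's estimate gives 0.10 × 142 = 14.2, so at most about 14 subjects.

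**3. Effect on the month-3 difference.** Let w be the share withdrawn, c the mean change in compliers and n the mean change non-compliers would have shown if followed. Subscripts A and P denote active and placebo.

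- As planned (withdrawn subjects set to 0): (1 − w_A)c_A − (1 − w_P)c_P
- If followed: add w_A n_A − w_P n_P

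The Protocol gives no values for c, n or w by arm. Assumed: c_A = −2.5, c_P = −1.5, n_A = −1.25, n_P = −0.75 days.

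| Withdrawn, active / placebo | If followed | As planned |
|---|---|---|
| 5% / 5% | −2.4375 + 1.4625 = −0.975 | −2.375 + 1.425 = −0.95 |
| 10% / 10% | −2.375 + 1.425 = −0.95 | −2.25 + 1.35 = −0.90 |
| 15% / 5% | −2.3125 + 1.4625 = −0.85 | −2.125 + 1.425 = −0.70 |
| 5% / 15% | −2.4375 + 1.3875 = −1.05 | −2.375 + 1.275 = −1.10 |

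The third row understates the followed difference by 0.15 / 0.85 = 18%. The fourth overstates it by 0.05 / 1.05 = 5%.

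**4. Same question in SD units.** With 10% withdrawn in each arm, 0.50 SD becomes 0.90 × 0.50 = 0.45 SD. With 71 per arm, normal-approximation power is 0.80, 0.78 or 0.75 for an assumed placebo improvement of 0, 0.5 or 1.0 SD. It is 0.85 if all 142 are followed. That last figure assumes non-compliers respond like everyone else, so the gap is an upper figure.

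**5. No true effect.** Assume both arms improve by 1.0 SD, non-compliers included, and 15% of active and 5% of placebo subjects are withdrawn. The expected improvement in active is then lower by (0.15 − 0.05) × 1.0 = 0.10 SD. The variances are 0.85 + 0.85 × 0.15 = 0.9775 and 0.95 + 0.95 × 0.05 = 0.9975, so SE = √(1.975 / 71) = 0.167. Two-sided rejection is about 0.09 instead of 0.05. The reverse imbalance gives the same size of bias in favour of active.

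**6. The two thresholds.** Four caplets a day for 28 days is 112 caplets. Then 0.80 × 112 = 89.6 and 0.85 × 112 = 95.2, so a subject who takes 90 to 95 caplets meets one figure and fails the other.

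**The case against.** Several stronger conclusions are tempting, and the Protocol does not support them.

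- *These subjects are deleted from the analysis.* A subject withdrawn at Visit 3 or 4 normally has a dose and a post-treatment measurement, so stays in the mITT population in the assigned arm. What is lost is the observed value.
- *Nothing is collected after withdrawal.* Adverse events present at withdrawal are followed, non-serious events are collected for 14 days after treatment stops, serious events are followed for at least 2 weeks after the last dose, and pregnancies are followed to delivery. Only efficacy follow-up is absent.
- *All plan violators are removed.* They may be dropped, at discretion.
- *The missing Visit 5 threshold loses month-3 data.* Visit 5 is the exit visit and that diary period is over. The only consequence is the unequal handling of non-compliers by month.
- *Compliance withdrawals use up the whole 10% allowance.* The Protocol does not say whether they lie inside or on top of the early-termination rate.
- *The waiver lets people who know the assignment choose whose outcome is kept.* The trial is double-blind and no section says that those granting approval know the allocation. The waiver can only retain subjects. The valid criticism is that it has no criterion.

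Two further objections stand in part. Every loss in the working comes through the baseline imputation, so these figures should not be added to those of a separate point on that method. The need for diary follow-up remains under any imputation. Also, the 80% rule is written for the medication returned at the next visit, so its use at Visit 4 is a reading of the text, which is one more reason to reconcile the passages.

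**Conclusion.** The point holds in a limited form. As written, the Protocol loses observable primary data because of a post-randomisation behaviour and puts a zero change in their place. At the ceiling of its own estimate this affects about 14 of 142 subjects.

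Under the assumed changes, the error is small when the arms lose equal shares (0.05 days at 10%/10%, 0.025 at 5%/5%). It grows to 0.15 days against active at 15%/5%, and is 0.05 days in favour of active at 5%/15%. These sizes rest on assumed changes, assumed arm-specific withdrawal and non-compliers achieving half the compliers' change. The mechanism and the unknown direction do not depend on those values.

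The 80% and 85% statements contradict each other or leave the trigger undefined, and must be reconciled. Which figure is intended cannot be settled from the document. The Protocol should be changed on both counts.

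**What to change.** Limit the change to data collection and to the use of the data collected:

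1. In Visit 2, item 9 and in Discontinuation/Withdrawal from Study, state that a subject withdrawn for low medication compliance, or dropped for a plan violation, is asked to keep completing the existing e-diary to the end of month 3 unless consent is withdrawn.
2. In the imputation paragraph, state that observed month-3 diary data from these subjects are used in the primary analysis in place of the baseline value.
3. Report adherence in all three months descriptively or in a sensitivity analysis. Drug accountability and the diary's study-medication item already capture it.
4. Reconcile Visit 2, item 9 with item 7 of Visits 3 and 4, and say what follows from a failed check and at which visits.

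Decisions on study medication, and withdrawals for safety or pregnancy, stay with the clinical sections. Once the diary continues, the approval waiver no longer decides whether a month-3 outcome can be observed.

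The cost is Protocol wording, modest follow-up work at the sites and some diary data recorded off study medication.
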